6.2 Usage of Concurrent/Concomitant Medications

Though no specific concomitant medications are prohibited during this study (other than concomitant anti-tumor therapies), vismodegib may potentially affect the pharmacokinetics of other drugs by altering their metabolism. In addition, metabolic inducers could possibly modify the pharmacokinetics of vismodegib. Therefore, concomitant medications should be used with care, and the risk benefit profile of each agent should be taken in to consideration.

Vismodegib inhibits CYP2C8, CYP2C9, and CYP2C19 drug metabolism enzymes in vitro at clinically relevant concentrations. Caution should be exercised and dose reduction of the concomitant substrate drug should be considered when dosing vismodegib concurrently with medications with narrow therapeutic windows that are substrates of CYP2C8, CYP2C9, and CYP2C19, because their concentrations may become elevated and their effects increased or prolonged.

Vismodegib did not significantly inhibit CYP3A4 at clinically relevant concentrations in vitro; however, the clinical impact of vismodegib on substrates of CYP3A4 is unknown. Vismodegib is a substrate of CYP3A4; however, the in vitro metabolic conversion of vismodegib is low. Effects of CYP inducers (i.e., carbamazepine, phenobarbital, phenytoin, rifabutin, rifampin, St John's wort, and troglitazone) on clinical concentrations of vismodegib are unknown; it is possible that these drugs could reduce concentrations of vismodegib. Likewise, the effects of strong inhibitors of CYP3A4 (i.e., clarithromycin, erythromycin, itraconazole, ketoconazole, nefazodone, telithromycin) on vismodegib clinical concentrations are unknown; it is possible that these drugs could increase the concentrations of vismodegib. Use of these drugs should be documented.

The table in Appendix 5 lists substrate drugs in columns under the designation of specific cytochrome P450 isoforms. A drug appears in a column if there is published evidence that it is metabolized, to a clinically relevant degree by that isoform or in the FDA table of in vivo substrates for study. This is not necessarily a complete list; other medications may also interact with vismodegib.

7 Reporting and Documentation of Results

Measurable lesions are those that can be accurately measured in at least one dimension as ≥ 20 mm with CT or MRI scan or on color photographs. Patients will undergo tumor assessments per RECIST tumor response criteria outlined below. No central review of imaging data will be required due to the visual clarity in identifying the lesions and the consistent method of assessment to be used by all participating sites.

Prior radiation therapy is acceptable but there cannot be major overlap of the previously irradiated tissues with the new radiation treatment volumes anticipated to be delivered for the purposes of this protocol, in such a way that curative intent with radiation cannot be met. Furthermore, the total dose from all radiation delivered and expected to be delivered should not exceed the suggested dose constraints given for normal structures.

To ensure a valid comparison of tumor data and uniformity in the assessment of tumor response and disease progression, the following procedures should be implemented.

The same local physician should perform all physical tumor assessment evaluations for an individual patient. Radiologic interpretation should be performed by designated faculty members with experience in describing skin lesions.

All lesions (target and non-target) identified at baseline will be reassessed according to the imaging schedule provided in Table 6-1. The same method of evaluation (either CT scan or

MRI), and/or color photography in the case of skin lesions, if feasible, must be used from baseline until the end of the study.

7.1 Evaluation of Efficacy (or Activity)

A new cutaneous BCC will be considered as progressive local-regional disease (locally or regionally relapsed) if the lesion is > 5 mm, within the PTVs, and can be clearly documented as not being previously present. The new lesion should be biopsied but will be considered as PD unless confirmed on biopsy not to be consistent with BCC. If the new cutaneous lesion is not biopsied or the histology is inconclusive, it should be considered to be BCC and indicative of PD. Significant enlargement of a cutaneous BCC that was present at baseline should also be considered as PD.

If imaging shows a high likelihood of distant metastases (investigators are highly encouraged to contact one of the Principal Investigators with any questions in this matter), ongoing protocol-prescribed therapy may be terminated based on evaluation of potential clinical benefits versus risks to the patient, as assessed by the study investigator. The patient may still be eligible for follow-up, per stipulations in section 6.1.5. New distant metastatic lesions should be biopsied if possible and will be considered as PD unless confirmed on biopsy not to be consistent with BCC. If the new metastatic lesion is not biopsied or the histology is inconclusive, it should be considered to be indicative of PD.

Note: Information about patients who have progressed on study and been removed from study may be voluntarily submitted at the discretion of the treating investigator (see Section 6.1.5).

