7.2.1.2 Disease Parameters

Measurable disease

Measurable disease is defined as lesions (or tumors) that can be accurately measured in at least one dimension (longest diameter to be recorded) with a minimum size of 10mm by CT scan (irrespective of scanner type) and MRI (no less than double the slice thickness and a minimum of 10mm), 10mm caliper measurement by clinical exam (when superficial), and/or 20mm by chest X-ray (if clearly defined and surrounded by aerated lung).

Tumor measurements will be performed measuring the maximal diameter as the maximal extent of tumor plus any adjacent or underlying ulceration. All tumor measurements will be recorded in millimeters or decimal fractions of centimeters. Previously irradiated lesions are considered non-measurable except in cases of documented progression of the lesion since the completion of radiation therapy.

Target lesions

All measurable lesions up to a maximum of 5 lesions total (and a maximum of two lesions per organ) representative of all involved organs should be identified as target lesions and recorded and measured at baseline. Target lesions will be selected on the basis of their size (lesions with the longest diameter) and their suitability for accurate repeated measurements (either by imaging techniques or clinically). A sum of the longest diameter (LD) for all target lesions will be calculated and reported as the baseline sum LD. The baseline sum LD will be used as reference by which to characterize the objective tumor response.

Non-measurable disease

Non-measurable disease is all other lesions (or sites of disease), including small lesions (longest diameter <20 mm with conventional techniques or < 10 mm using spiral CT scan). Leptomeningeal disease, ascites, pleural or pericardial effusion, inflammatory breast disease, lymphangitic involvement of skin or lung, abdominal masses/abdominal organomegaly identified by physical exam that is not measurable by reproducible imaging techniques are all non-measurable.

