7.2.1.4 Response Criteria

Evaluation of Target Lesions

Complete Response (CR)

Disappearance of all target lesions in the irradiated PTV, determined by two separate observations conducted not less than 4 weeks apart. Any pathological lymph nodes (whether target or non-target) must have reduction in short axis to <10 mm (the sum may not be “0” if there are target nodes). There can be no appearance of new lesions in irradiated PTV.

Partial Response (PR)

At least a 30% decrease in the sum of the longest diameter (LD) of target lesions in the irradiated PTV, taking as reference the baseline sum LD. There can be no appearance of new lesions in irradiated PTV.

Progressive Disease (PD)

At least a 20% increase in the sum of the SLD of target lesions, taking as reference the smallest sum SLD recorded since the treatment started and minimum 5 mm increase over the nadir, or the appearance of one or more new lesions in the irradiated PTV.

Stable Disease (SD)

Neither sufficient shrinkage to qualify for PR nor sufficient increase to qualify for PD, taking as reference the smallest sum LD since the treatment started.

Evaluation of Best Overall Response

The best overall response is the best response recorded from the start of the treatment until disease progression/recurrence (taking as reference for PD the smallest measurements recorded since the treatment started). The patient's best response assignment will depend on the achievement of both measurement and confirmation criteria.

Table 7.1 Response Criteria

Target Lesions	Non-Target Lesions	New Lesions	Overall Response	Best Response for this Category Also Requires
CR	CR	No	CR	> 4 weeks confirmation
CR	Non-CR/ Non-PD	No	PR	> 4 weeks confirmation
PR	Non-PD	No	PR	
SD	Non-PD	No	SD	documented at least once > 4 weeks from baseline
PD	Any	Yes or No	PD	no prior SD, PR or CR
Any	PD*	Yes or No	PD	
Any	Any	Yes	PD	

* In exceptional circumstances, unequivocal progression in non-target lesions may be accepted as disease progression. These circumstances should be discussed with the Principal Investigators.

Duration of Response

Duration of overall response

The duration of overall response is measured from the time measurement criteria are met for CR or PR (whichever is first recorded) until the first date that recurrent or PD is objectively

documented (taking as reference for PD the smallest measurements recorded since the treatment started).

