8.2 Study Endpoints

Primary Endpoint:

- The proportion of patients with local-regional control at 12 months from protocol therapy completion, defined as complete or partial response, with absence of PD (see section 7.2) within the irradiated PTV.

Secondary Endpoints:

- Estimate of the probability of PFS and OS 12 months after protocol therapy completion. PFS is measured until disease recurrence or death due to any cause, whichever occurs first.
- Number and attribution of all adverse events (including vital signs, physical findings, and clinical laboratory results, CTCAE, v 4.0) in patients who receive any amount of study drug and radiation therapy.
- For each toxicity, the maximum occurring grade will be tabulated for each patient. The results will be summarized by toxicities observed during vismodegib treatment alone, during concurrent vismodegib with radiation therapy, for 3 months immediately following the completion of protocol therapy and for up to 12 months after completion of protocol therapy. The focus will be on the proportion of patients experiencing \geq grade 3 toxicity during each of these intervals.
- Proportion of patients experiencing Grade 4-5 adverse events assessed to be definitely, probably, or possibly related to the induction or concurrent treatment components of the protocol regimen (that is not definitely related to disease progression).
- Proportion of patients discontinuing treatment due to toxicity during the concurrent administration of vismodegib and radiation therapy. For this endpoint, discontinuation is defined as $<$ 75% of planned radiation therapy delivered.
- Response rate per RECIST criteria in patients who complete initial combined therapy of the primary site and regionally involved areas in subjects with measurable disease prior to initiation of therapy at 3 months after completion of protocol therapy.
- Proportion of patients with a decrease of BCC within the irradiated PTV after completing all protocol therapy to estimate clinical response to vismodegib and radiation therapy.

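### Local-regional progression is defined in three ways, and the one the primary endpoint cites pools the target lesions, so marked regrowth of one irradiated lesion can be scored as control

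*Combined protocol and SAP*

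**What the plan says.** **Endpoint.** Section 8.2 takes local-regional control at 12 months as "defined as complete or partial response, with absence of PD (see section 7.2) within the irradiated PTV". Section 8.5 repeats it as CR or PR by RECIST and does not mention 7.1. Sections 2.1 and 2.3.1 state the same endpoint without pointing to any section for PD.

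**Rule 1, section 7.1.** "Significant enlargement of a cutaneous BCC that was present at baseline should also be considered as PD". This works lesion by lesion and is limited to cutaneous tumours. It is not limited to target lesions, gives no size of increase, and does not say whether growth is judged from baseline or from nadir.

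**Rule 2, section 7.2.1.4.** PD is "At least a 20% increase in the sum of the SLD of target lesions, taking as reference the smallest sum SLD recorded" since treatment started, with a "minimum 5 mm increase over the nadir, or the appearance of one or more new lesions in the irradiated PTV". PR is pooled as well: "At least a 30% decrease in the sum of the longest diameter (LD) of target lesions in the irradiated PTV". Table 7.1 has rows for non-target progression and for new lesions. It has none for a single target lesion that enlarges while the sum does not.

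**Rule 3, section 7.3.** Local or regional progression is growth of more than 20% in the product of two perpendicular diameters of the tumour over the smallest earlier value, or new areas of disease. The text does not say whether this is applied to each lesion.

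**Number of lesions.** Section 7.2.1.2 sums "All measurable lesions up to a maximum of 5 lesions total", with at most two per organ. The note to exclusion criterion 11 (3.3.2) lets a treated area hold more than one lesion, and inclusion criterion 1 (3.3.1) admits involved neck nodes.

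**The concern.** Control within the irradiated volume is lost when any irradiated lesion regrows, and section 8.5.1 defines failure in terms of the treated PTV. A pooled sum measures total tumour burden instead. Where two or more target lesions lie in the PTV, shrinkage of a large one can absorb growth of a smaller one. The patient then has PR without PD under the rule that 8.2 cites, and PD under 7.1.

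The primary test has 24 patients, and no central review is planned (section 7). The scoring of a patient on whom the rules disagree would therefore be settled locally, with an unquantified *significant* on one side and a sum on the other. The same records could give different primary results depending on which section a reader follows.

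**Working it through.** **1. The plan's own figure.** Section 8.3.1 gives 24 evaluable patients, null 60%, alternative 80%, one-sided 0.10, exact binomial test and 81% power.

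- P(X ≥ 18 | 24, 0.60) = 0.0960 and P(X ≥ 17 | 24, 0.60) = 0.1919, so 18/24 rejects and 17/24 does not.
- P(X ≥ 18 | 24, 0.80) = 0.8111, which reproduces the stated 81%.

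**2. Can the rules disagree?** Assume two target lesions, A and B, both in the PTV (diameters in mm are illustrative).

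| Time | A | B | Sum |
|---|---|---|---|
| Baseline | 80 | 20 | 100 |
| Nadir | 45 | 12 | 57 |
| 12 months | 40 | 28 | 68 |

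- Sum over nadir: 68/57 − 1 = +19.3%. The 5 mm condition is met (68 − 57 = 11) but the 20% condition is not, so this is not PD.
- Sum against baseline: 68/100 − 1 = −32%, so PR.
- Lesion B: 28/12 − 1 = +133% over its nadir and 28/20 − 1 = +40% over its baseline.

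Section 7.2.1.4 scores control. Section 7.1 scores PD on any sensible reading of *significant*, whether baseline or nadir is the reference.

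**3. Does this depend on being close to the cut-off?** That example is close: the PD threshold is 1.2 × 57 = 68.4 mm, and B at 29 mm gives 69/57 − 1 = +21%, which is PD. A second series is not close:

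| Visit | A | B | Sum | Against baseline | Against prior nadir |
|---|---|---|---|---|---|
| Baseline | 60 | 20 | 80 | – | – |
| Week 13–14 | 36 | 22 | 58 | −27.5% | −27.5% |
| End of treatment | 28 | 28 | 56 | −30.0% | −3.4% |
| 3 months | 20 | 34 | 54 | −32.5% | −3.6% |
| 6 months | 14 | 38 | 52 | −35.0% | −3.7% |
| 12 months | 10 | 42 | 52 | −35.0% | 0.0% |

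B grows by 42/20 − 1 = 110%. The sum never rises above its nadir and the patient is in PR at 12 months.

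**4. When it cannot happen.**

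- With one target lesion the sum is that lesion, so nothing can be offset.
- For B to double while the sum still meets PR, even with A gone, 2B ≤ 0.7(A + B). Hence A ≥ (1.3/0.7)B = 1.86B at baseline.
- If A shrinks early, the nadir rule catches the regrowth. With 60+20 at baseline, 15+20 = 35 at week 13–14 and 10+36 = 46 at 6 months, 46/35 − 1 = +31%, which is PD.

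**5. Section 7.3 against 7.2.1.4.** If both diameters grow equally, the product reaches +20% when each has grown by √1.20 − 1 = 9.5%. Section 7.3 can therefore call progression at less than half the 20% diameter increase that 7.2.1.4 requires, even with a single lesion.

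**6. Direction.** A single-lesion clause added to 7.2.1.4 can add PD calls and remove none. Leaving it out can only move patients from failure to control.

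**7. Sensitivity.** Let k be the share of true failures scored as control, at a true rate of 60%. The observed rate is 0.60 + 0.40k. Expected true failures are 24 × 0.40 = 9.6.

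| k (assumed) | Expected masked patients | Observed rate | P(X ≥ 18) |
|---|---|---|---|
| 0 | 0 | 0.600 | 0.096 |
| 2% | 0.19 | 0.608 | 0.110 |
| 5% | 0.48 | 0.620 | 0.134 |
| 10% | 0.96 | 0.640 | 0.182 |

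The documents supply no value of k.

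**The case against.** **Section 7.1 may already apply.** It stands under the efficacy heading and says that enlargement *also* counts as PD, which can be read as adding to the sum rule. Sections 2.1 and 2.3.1 state the endpoint without restricting PD to 7.2. This stands as a fair reading. A reader might infer that the plan definitely counts in-field regrowth as success; the documents do not support that. They leave the matter open: the only section reference for PD in the endpoint definition is to 7.2, and neither 7.2.1.4 nor 8.5 carries the 7.1 rule over. Even on the additive reading, 7.1 lacks a threshold and a reference.

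**The pattern is narrow.** It needs two or more target lesions in the PTV with opposing trends, and the cap of two per organ may limit how many skin lesions are pooled. This stands, and it limits the frequency. That one patient can move the result from 17/24 to 18/24 is true of any misclassification at this sample size.

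**Section 7.1 is not as wide as it looks.** One might read it as making any growth of any baseline BCC progression. It says *significant* and *cutaneous*, and it may be aimed partly at non-target lesions, which Table 7.1 already covers.

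**Summing is the RECIST convention.** A single-lesion clause departs from it and has a cost. Section 7.2 counts adjacent or underlying ulceration in the diameter, so ulceration around a small residual lesion could be called PD. This stands as a cost. It does not remove the conflict, because 7.1 already contains a single-lesion rule.

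**Conclusion.** The point holds as a conflict between definitions that bears on the primary endpoint. Sections 7.1, 7.2.1.4 and 7.3 set different rules for local-regional progression, 8.2 cites only 7.2, and nothing says which rule prevails. In patients with at least two target lesions in the PTV, 7.2.1.4 can score control where 7.1 scores PD. Any resulting error favours success.

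The size is unknown. The type I error range of 0.096 to 0.182 rests on assumed masking of 0 to 10% of true failures. A reader might take it as an estimate of bias in this trial, but the documents give neither the number of patients with several target lesions nor how often lesions diverge, so the effect may be close to nil. Nor is every rise of up to one fifth of the nadir sum missed: exactly 20%, such as 10 mm on a nadir of 50 mm or 16 mm on 80 mm, is PD under 7.2.1.4.

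The wording should be settled before the primary endpoint is scored, because it decides how individual patients count where 18/24 rejects (p = 0.096) and 17/24 does not (p = 0.192).

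**What to change.** For scoring the primary endpoint only:

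1. In 8.2 and 8.5, cite 7.1 as well as 7.2 for the meaning of PD.
2. In 7.2.1.4, add that for local-regional control PD is also met when any single target lesion in the PTV enlarges beyond one stated threshold over its own smallest recorded diameter, whatever the sum does. The plan's own 20% and 5 mm would serve.
3. In 7.1, use the same threshold and reference for target lesions, and leave non-target lesions to the standard in Table 7.1.
4. Reconcile the bidimensional rule in 7.3 with these, or state that it does not govern the primary endpoint.

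The change does not address when a patient stops treatment or leaves the study.

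**Cost.** Only protocol and SAP wording changes. Section 7.2 already requires every originally assessed tumour to be measured, and the sample size, alpha and power stay as planned. The downside is that measurement error in a single lesion, including ulceration counted in its diameter, may add a few PD calls and make the control rate slightly less favourable.

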7.2 Antitumor Effect – Solid Tumors

Response and progression in this study will be evaluated using the new international criteria proposed by the Response Evaluation Criteria in Solid Tumors ([RECIST](#)) Committee [JNCI 92(3):205-216, 2000]. Assessments should include an evaluation of all sites of disease. Patients will undergo tumor assessments per RECIST tumor response criteria. Screening digital photographs of visible portions of the lesions may be taken any time from the start of screening until just prior to dosing on Day 1. Tumor measurements will be performed measuring the maximal diameter as the maximal extent of tumor plus any adjacent or underlying ulceration. Any tumors which were included in the original assessment as either a primary involved site or involved regional lymph node must be measured.

7.2.1.1 Definitions

Evaluable for toxicity

All patients receiving any study drug will be evaluable for toxicity from the time of their first treatment with the study drug.

Evaluable for objective response

Only those patients who have measurable disease present at baseline, have completed at least 75% of protocol-mandated radiotherapy, and have had their disease re-evaluated will be considered evaluable for response. These patients will have their response classified according to the definitions stated below. (Note: Patients who exhibit objective disease progression prior to the end of induction therapy will also be considered evaluable.)

7.2.1.2 Disease Parameters

Measurable disease

Measurable disease is defined as lesions (or tumors) that can be accurately measured in at least one dimension (longest diameter to be recorded) with a minimum size of 10mm by CT scan (irrespective of scanner type) and MRI (no less than double the slice thickness and a minimum of 10mm), 10mm caliper measurement by clinical exam (when superficial), and/or 20mm by chest X-ray (if clearly defined and surrounded by aerated lung).

Tumor measurements will be performed measuring the maximal diameter as the maximal extent of tumor plus any adjacent or underlying ulceration. All tumor measurements will be recorded in millimeters or decimal fractions of centimeters. Previously irradiated lesions are considered non-measurable except in cases of documented progression of the lesion since the completion of radiation therapy.

Target lesions

All measurable lesions up to a maximum of 5 lesions total (and a maximum of two lesions per organ) representative of all involved organs should be identified as target lesions and recorded and measured at baseline. Target lesions will be selected on the basis of their size (lesions with the longest diameter) and their suitability for accurate repeated measurements (either by imaging techniques or clinically). A sum of the longest diameter (LD) for all target lesions will be calculated and reported as the baseline sum LD. The baseline sum LD will be used as reference by which to characterize the objective tumor response.

Non-measurable disease

Non-measurable disease is all other lesions (or sites of disease), including small lesions (longest diameter <20 mm with conventional techniques or < 10 mm using spiral CT scan). Leptomeningeal disease, ascites, pleural or pericardial effusion, inflammatory breast disease, lymphangitic involvement of skin or lung, abdominal masses/abdominal organomegaly identified by physical exam that is not measurable by reproducible imaging techniques are all non-measurable.

